## Results

As regard index cases, there were 9 (11.8%) mild , 44 (57.9%) moderate and 23 (30.3%) severe cases. In the ivermectin group, there were 8 (53.3%) mild , 6 (40%) moderate and 1 (6.7%) severe cases. While in the no-intervention group, there were 31 (52.5) mild, 21 (35.6%) moderate and 7 (11.9%) cases.

[figure not shown]

Figure (1): Scatter plot shows relationship between contact time in days and number of contacts that developed COVID-19; dashed line represent best fitted line (quadratic model).

There was insignificant linear correlation between contact time in days and number of contact that developed COVID-19. The appropriate forecasting for number of contact that developed COVID-19 based upon contact time in days was quadratic model.

[figure not shown]

Figure (2): Box plot shows relationship between isolation and number of contacts that developed COVID-19.

There was insignificant difference between index cases isolated at hospital and index cases isolated at home regarding number of contact that developed COVID-19 where mean number of contact that developed COVID-19 ( $\pm$ SD) was 2.14 ( $\pm$ 1.35) versus 2.07 ( $\pm$  2.26) respectively (p-value=0.280)

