**Table (1): Comparison between Ivermectin arm and non-intervention arm regarding basic characteristics.**

| Basic characteristics  | Ivermectin arm
(N=203) |       | Non-intervention arm
(N=101) |       | Test       | p-value |
|------------------------|---------------------------|-------|---------------------------------|-------|------------|---------|
|                        | No.                       | %     | No.                             | %     |            |         |
| Gender          |                           |       |                                 |       |            |         |
| Male                   | 106                       | 52.2% | 50                              | 49.5% | 0.199a     | 0.656   |
| Female                 | 97                        | 47.8% | 51                              | 50.5% |            |         |
| Age (years)     |                           |       |                                 |       |            |         |
| Mean ± SD              | 39.75 ± 14.93             |       | 37.69 ± 16.95                   |       | -          | 0.175   |
| Median (Range)         | 38 (16 – 94)              |       | 35 (16 – 78)                    |       | 1.357
b |         |
| Any comorbidity |                           |       |                                 |       |            |         |
| Absent                 | 156                       | 76.8% | 75                              | 74.3% | 0.248a     | 0.619   |
| Present                | 47                        | 23.2% | 26                              | 25.7% |            |         |

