**a: Chi-square test; b: Mann Whitney U test; p< 0.05 is significant.**

**Table (2)** shows that 15 contacts (7.4%) developed COVID-19 in the ivermectin arm compared to 59 (58.4%) in the no-intervention arm, all of them were symptomatic, according to the study protocol . The difference was highly significant ( $p<0.001$ ). The median (range) days for developing the disease was 2 (2-6) in ivermectin group compared and 4 (2-10) in the no-intervention group, the difference was significant ( $p<0.017$ ). Ten contacts (66.6%) developed symptoms in 1st 3 days in ivermectin group, and none developed it after 6 days. In the no-intervention arm, 25 (42.3%) developed symptoms in the 1st 3 days and continued to the 10 days.

HRCT of the chest was performed in 14 out 15 contacts and in 58 of the 59 contacts who developed symptoms in ivermectin and no-intervention groups, respectively. The missed one case in each arm had symptoms and positive RT-PCR without other investigations. Chest HRCT was positive for

COVID-19 in 7 (50%) and 28 (48.3%) in ivermectin and no-intervention groups, respectively.

Complete blood count was performed also in 14 and 58 contacts who developed symptoms in ivermectin and no-intervention groups respectively. Positive criteria in CBC was present in 12 (85.7%) and 53 (91.4%) in ivermectin and no-intervention groups respectively.

**Table (3): Comparison between Ivermectin arm and non-intervention arm regarding protection rate stratified by basic characteristics.**

|                     |          | Protection rate |                      | Testa  | p-value |
|---------------------|----------|-----------------|----------------------|--------|---------|
|                     |          | Ivermectin arm  | Non-intervention arm |        |         |
| All patients        |          | 92.6%           | 41.6%                | -----  | -----   |
| Index case severity | Mild     | 92.9%           | 35%                  | 11.381 | 0.001   |
|                     | Moderate | 95.6%           | 55.8%                | 42.666 | <0.001  |
|                     | Severe   | 85.2%           | 28.9%                | 29.928 | <0.001  |
| Age                 | ≤60      | 93.8%           | 41.3%                | 91.514 | <0.001  |
|                     | >60      | 84%             | 44.4%                | 5.320  | 0.034   |
| Gender              | Male     | 94.3%           | 42%                  | 53.482 | <0.001  |

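### The contact-time and isolation analyses use raw counts of infected contacts, without contacts at risk or arm and apparently on fewer than half of the index cases, so they cannot show whether exposure affects infection

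*Combined protocol and SAP*

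**What the plan says.** All references are to the combined protocol and SAP.

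- **Results, text under Figure (1):** "There was insignificant linear correlation between contact time in days and number of contact that developed COVID-19". It continues: "The appropriate forecasting for number of contact that developed COVID-19 based upon contact time in days was quadratic model". No correlation coefficient, p-value, fit statistic or number of index cases is given.
- **Results, text under Figure (2):** "There was insignificant difference between index cases isolated at hospital and index cases isolated at home regarding number of contact that developed COVID-19". The means (SD) are 2.14 (1.35) for hospital and 2.07 (2.26) for home, with p = 0.280. Group sizes are not given.
- **Results, opening paragraph, on index cases:** "there were 9 (11.8%) mild , 44 (57.9%) moderate and 23 (30.3%) severe cases".
- **Text under Table (2):** "15 contacts (7.4%) developed COVID-19 in the ivermectin arm compared to 59 (58.4%) in the no-intervention arm".
- **Statistical analysis:** lists the Mann-Whitney, chi-square and Fisher tests, relative risk and logistic regression. It describes no correlation, curve fit, count or rate model, or offset for contacts at risk.
- **Table (4):** the only adjusted model. It contains arm, index severity, age, gender and comorbidity, but neither contact time nor place of isolation.

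**The concern.** A count of infected contacts mixes the risk per contact with the number of contacts. At the same risk, a larger household gives a larger count. Arm is by far the strongest factor in the data. If household size or the share of contacts on ivermectin differs by place of isolation or length of contact, the raw count can hide an exposure effect or create one. Nothing elsewhere in the document repairs this.

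The functional form is also unplanned. A quadratic is called appropriate after the linear correlation was not significant, and no fit measure or interval supports it.

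What is at stake is limited but real. Contact time and isolation are the exposure variables that the text reports on, apart from index severity, and Table (1) compares the arms on neither. A reader could take the two non-significant results as reassurance that exposure did not matter.

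**Working it through.** **Inputs.** Index cases: 9 + 44 + 23 = 76 (Results, opening paragraph). Contacts: 203 + 101 = 304 (Table (1)). Infected: 15 + 59 = 74 (Table (2)). Isolation means, SDs and p-value: text under Figure (2).

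**1. Anchor.** Pearson chi-square on 188/15 v 42/59 gives 95.35, matching the stated 95.351. The infected counts by arm can be relied on. The risk ratio is (59/101)/(15/203) = 0.584/0.074 = 7.9.

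**2. The stated p-value.** p = 0.280 cannot be reproduced directly, because group sizes are missing. It is not in itself implausible; see step 6.

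**3. Why the denominator matters.** Contacts per index case average 304/76 = 4.0, but the spread is not given. With assumed household sizes, a count of 2.1 infected is an attack rate of 2.1/3 = 70%, 2.1/4 = 53% or 2.1/8 = 26%.

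**4. Can the means cover all index cases?** 76 × 2.07 = 157 and 76 × 2.14 = 163 infected contacts would be needed. Only 74 occurred, and 74/76 = 0.97 per index case. Allowing for rounding of the lower mean, the base is at most 74/2.065 = 35.8, that is 35 index cases.

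**5. Which split fits?** Counts are integers, so the mean must be a ratio of integers that rounds as stated. With at most 74 infected in total:

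| Hospital (infected/index cases) | Home (infected/index cases) | Total infected | Home SD of 2.26 possible? |
|---|---|---|---|
| 15/7 | 29/14 | 44 | no |
| 15/7 | 31/15 | 46 | no |
| 15/7 | 56/27 | 71 | no |
| 15/7 | 58/28 | 73 | yes |
| 30/14 | 29/14 | 59 | no |
| 30/14 | 31/15 | 61 | no |
| 45/21 | 29/14 | 74 | no |

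The hospital SD of 1.35 is attainable in every row. The SD test uses the usual n − 1 divisor and requires the sum of squared counts to be an integer of the right parity. Only 7 hospital (15 infected) plus 28 home (58 infected) survives: 35 index cases and 73 infected.

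**6. Consequences of that split.**
- Index cases not in the analysis: 76 − 35 = 41.
- Infected contacts left for those 41: 74 − 73 = 1. If each infected contact belongs to one index case, at least 40 of the 41 had none.
- 73 exceeds the 59 infected in the non-intervention arm, so at least 73 − 59 = 14 come from the ivermectin arm. Both arms are pooled.
- With at least one infected contact per home index case, count sets that fit this split give Mann-Whitney p-values from about 0.06 to 0.70, depending on the set and the version of the test. The stated value lies inside that range. With 7 hospital index cases the comparison is very imprecise.

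**The case against.** **The figures are missing from the text available.** Figures (1) and (2) and the content of the flow diagram are not shown. They may mark arm or give numbers of index cases. That stands as a limit on the criticism, but the written results report no arm-specific or adjusted finding.

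**No claim of no effect is made.** The text says only that the results were not significant. Contact time and isolation are not in the aim or objectives, and neither result is used in Tables (1) to (4). This is right, and it keeps the point secondary.

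**Confounding is not demonstrated.** A reader might infer that the two results are in fact confounded. The documents do not support that: household size and arm are not given by place of isolation or by contact time. The results may be confounded, and the reader cannot tell.

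**The size of the arm effect on these counts is unknown.** A reader might multiply 4 contacts by the two risks, get 0.30 v 2.34 infected, and conclude that arm alone produces an 8-fold spread here. That assumes all 76 index cases were analysed and that arm was constant within a household. Step 4 contradicts the first, and the documents do not state the second. If every analysed index case had at least one infected contact, the same inputs give 0.296/(1 − 0.926⁴) = 1.12 v 2.336/(1 − 0.416⁴) = 2.41, about 2.2-fold. Neither ratio should be quoted as the trial's bias.

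**The contact-level data may not exist.** No section shows that contact time was recorded per contact. This also stands, and the fix allows for it.

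**Conclusion.** The point holds as a fault in two secondary analyses. As reported, they have no contacts at risk and no arm, and cannot show whether exposure affects infection in either direction.

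That the isolation comparison covers at most 35 of 76 index cases needs only the stated means and the total of 74. The exact split (7 and 28), the 41 omitted index cases and the pooling of arms also need the SDs to be correctly reported. All of this assumes that the counts refer to the 304 trial contacts, each linked to one index case.

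That index cases were dropped because nobody around them was infected is an inference about the selection rule, not something the document states. If it is right, the analysis selects on its own outcome, and adjusting for arm and household size within the 35 would not cure it. Whether the contact-time analysis used the same subset is not stated.

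The direction and size of any bias cannot be computed from what is published. A reader might extend the point to the efficacy comparison; nothing here supports that, because Tables (2) to (4) do not use these results.

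**What to change.** 1. State how many index cases entered each analysis and how they were chosen.
2. Re-run on all 76 index cases, including those with no infected contact.
3. Model infection relative to contacts at risk, with arm, place of isolation and contact time as covariates. Either use Poisson regression with log(number of contacts) as offset and robust standard errors, or a contact-level logistic or log-binomial GEE clustered on index case. If any household contained both arms, use the contact-level form or split the count by arm.
4. Report estimates with 95% CIs rather than a statement of non-significance.
5. Label the quadratic curve as post hoc and exploratory, or drop it.
6. If contacts at risk per index case are not available, withdraw both statements.

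**Cost:** a little more analysis, provided that contacts, arm, isolation and contact time were recorded per index case, and the loss of the quadratic forecast. Label: cheap improvement, secondary.

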**Table (1): Comparison between Ivermectin arm and non-intervention arm regarding basic characteristics.**

| Basic characteristics  | Ivermectin arm
(N=203) |       | Non-intervention arm
(N=101) |       | Test       | p-value |
|------------------------|---------------------------|-------|---------------------------------|-------|------------|---------|
|                        | No.                       | %     | No.                             | %     |            |         |
| Gender          |                           |       |                                 |       |            |         |
| Male                   | 106                       | 52.2% | 50                              | 49.5% | 0.199a     | 0.656   |
| Female                 | 97                        | 47.8% | 51                              | 50.5% |            |         |
| Age (years)     |                           |       |                                 |       |            |         |
| Mean ± SD              | 39.75 ± 14.93             |       | 37.69 ± 16.95                   |       | -          | 0.175   |
| Median (Range)         | 38 (16 – 94)              |       | 35 (16 – 78)                    |       | 1.357
b |         |
| Any comorbidity |                           |       |                                 |       |            |         |
| Absent                 | 156                       | 76.8% | 75                              | 74.3% | 0.248a     | 0.619   |
| Present                | 47                        | 23.2% | 26                              | 25.7% |            |         |

**a: Chi-square test; b: Mann Whitney U test; p < 0.05 is significant.**

**Table (1)** shows that there was no significant difference between both arms as regard gender, age or comorbidities. The median (range) age for both groups was 38 (16-94) and 35 (16-78) years respectively.

The most common comorbidities were; hypertension in 16 (7.9%) and 13 (12.9%), DM in 13 (6.4%) and 10 (9.9%), bronchial asthma in 7 (3.4%) and 2 (2%), ischemic heart disease in 6 (3%) and 1 (1%), hypothyroidism in 5 (2.5%) and 1 (1%), chronic kidney disease in 2 (1%) and 1 (1%), liver

cirrhosis in 1 (0.5%) and 1 (1%), cardiomyopathy in 2 (1%) and 0% in both ivermectin and no-intervention group respectively.

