## Consort Flow diagram of Ivermectin prophylaxis trial

## **Statistical analysis**

All data were collected, tabulated and statistically analyzed using SPSS 22.0 for windows (IBM Inc., Chicago, IL, USA) and MedCalc 13 for windows (MedCalc Software Bvba, Ostend, Belgium). Continuous Quantitative variables were expressed as the mean  $\pm$  SD & median (range), and categorical qualitative variables were expressed as absolute frequencies (number) & relative frequencies (percentage). Continuous data were checked for normality by using Shapiro Walk test. Mann-Whitney U test was used to compare between two groups of non-normally distributed data. Categorical data were compared using Chi-square test or Fisher's exact test when appropriate. Relative risk and its 95%Confidence interval (CI) was calculated to estimate risk of COVID-19 infection in addition forest plot was plotted. Univariate and multivariate binary logistic regression were built to find predictors for COVID-19 protection. All tests were two sided. p-value < 0.05 was considered statistically significant.

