**a: Chi-square test; p< 0.05 is significant.**

**Table (3)** shows that 7.4% contacts developed diseases in ivermectin group while they were 58.4% in no-intervention group. Contacts tend to be infected when the index case was severe; 14.8% and 71.1% in both groups, respectively. The protection rate for ivermectin was more prominent in contacts less than 60 years old (6.2% infected compared to 58.7% if no intervention) , but still effective in elder than 60 years (16% infected compared to 55.6% if no intervention).

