**Table (4): Predictors for COVID-19 protection.**

|                            | Univariate Model      |         | Multivariate Model    |         |
|----------------------------|-----------------------|---------|-----------------------|---------|
|                            | OR (95%CI)            | p-value | OR (95%CI)            | p-value |
| Arm                 |                       |         |                       |         |
| Ivermectin                 | 12.533 (7.408-21.205) | <0.001  | 11.445 (4.444-29.475) | <0.001  |
| Non-intervention           | Reference             |         |                       |         |
| Index case severity |                       |         |                       |         |
| Mild                       | 1.429 (0.722-2.828)   | 0.306   | 1.257 (0.486-3.247)   | 0.637   |
| Moderate                   | 6.120 (4.010-9.341)   | <0.001  | 2.816 (1.355-5.851)   | 0.006   |

| Severe          | Reference           |        |                     |       |
|-----------------|---------------------|--------|---------------------|-------|
| <hr/>           |                     |        |                     |       |
| Age             |                     |        |                     |       |
| Age≤60 years    | 3.154 (2.386-4.169) | <0.001 | 0.254 (0.101-0.639) | 0.004 |
| Age>60 years    | Reference           |        |                     |       |
| <hr/>           |                     |        |                     |       |
| Gender          |                     |        |                     |       |
| Male            | 3.457 (2.373-5.036) | <0.001 | 0.836 (0.437-1.600) | 0.588 |
| Female          | Reference           |        |                     |       |
| <hr/>           |                     |        |                     |       |
| Any comorbidity |                     |        |                     |       |
| Absent          | 3.812 (2.774-5.239) | <0.001 | 2.222 (0.967-5.108) | 0.060 |
| Present         | Reference           |        |                     |       |

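### Index-case severity differs between the arms but is missing from Table 1, so the crude 7.4% v 58.4% modestly overstates the contrast

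*Combined protocol and SAP*

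**What the plan says.** - **Baseline comparison.** Table (1) compares the arms on gender, age and any comorbidity only. The text beneath it concludes that "there was no significant difference between both arms as regard gender, age or comorbidities".
- **Headline.** Table (2) and its text give the unadjusted result: "15 contacts (7.4%) developed COVID-19 in the ivermectin arm compared to 59 (58.4%) in the no-intervention arm", chi-square 95.351.
- **Severity of the index case.** The Results open with 9 mild, 44 moderate and 23 severe index cases, 76 in all and not split by arm. The per-arm counts that follow (8, 6, 1 and 31, 21, 7) add to 15 and 59, so they describe the contacts who fell ill and not the index cases.
- **Severity and outcome.** Table (3) gives protection rates by arm within each severity level, as percentages without denominators. Its text says "Contacts tend to be infected when the index case was severe; 14.8% and 71.1% in both groups, respectively".
- **Adjustment.** The multivariate column of Table (4) includes index-case severity and gives an odds ratio for arm of 11.445 (4.444 to 29.475). The univariate column prints 12.533 for arm.

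**The concern.** The stated aim is prevention of illness in contacts of a COVID-19 case, and the severity of that case is a feature of the exposure. The document itself links severity to infection. The Materials and Methods describe the design only as interventional, so balance on this factor cannot be presumed and has to be shown. Table (1) does not show it, and no table gives the number of contacts by index-case severity in each arm.

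If the arms differ on severity, part of the headline difference reflects the mix of index cases and not the drug. A reader who relies on Table (1) and the crude percentages cannot see this. Table (4) is the natural place to look for an adjusted answer, so whether its columns can be trusted also matters.

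**Working it through.** **1. Reproduce the crude result.** From Table (2), 188 protected and 15 ill v 42 and 59. Pearson chi-square without correction = 304 × (188×59 − 15×42)² / (203×101×230×74) = 95.351, as printed. Risk difference = 59/101 − 15/203 = 51.0 points. Relative risk (RR) = 0.126. Odds ratio (OR) of protection = 188×59/(15×42) = 17.6 (95% CI 9.1 to 34.0).

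**2. Rebuild the severity strata.** All whole-number counts were searched that match the Table (3) percentages and sum to 188/203 and 42/101. Each arm has exactly one solution:

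| Index case | Ivermectin protected | Ill | Non-intervention protected | Ill | Chi-square |
|---|---|---|---|---|---|
| Mild | 13/14 | 7.1% | 7/20 | 65.0% | 11.381 |
| Moderate | 129/135 | 4.4% | 24/43 | 44.2% | 42.666 |
| Severe | 46/54 | 14.8% | 11/38 | 71.1% | 29.928 |

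All three chi-squares equal those printed. The cells also return Table (4)'s univariate severity entries: (13+7)/(1+13) = 20/14 = 1.429 and (129+24)/(6+19) = 153/25 = 6.120.

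**3. Compare the arms on severity.** Ivermectin 14/135/54 of 203 (6.9%/66.5%/26.6%); non-intervention 20/43/38 of 101 (19.8%/42.6%/37.6%). Chi-square 19.35 on 2 df, p = 0.00006 if contacts were independent. They are not: 304 contacts share 76 index cases, about 4 each, and severity is common to a household. Dividing the chi-square by assumed design effects of 2, 3, 4 and 5 gives p = 0.008, 0.040, 0.089 and 0.144.

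**4. Standardise.** Weight each arm's stratum risks by a common severity mix.

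| Standard mix | Ivermectin | Non-intervention | Difference (points) | RR |
|---|---|---|---|---|
| None (crude) | 7.4% | 58.4% | 51.0 | 0.126 |
| Ivermectin arm (14/135/54) | 7.4% | 52.8% | 45.4 | 0.140 |
| All contacts (34/178/92) | 7.9% | 54.6% | 46.8 | 0.144 |
| Non-intervention arm (20/43/38) | 8.9% | 58.4% | 49.5 | 0.152 |

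For example, the non-intervention risk on the all-contacts mix = (34×0.650 + 178×0.442 + 92×0.711)/304 = 54.6%. Differences are taken before rounding. The shift from crude runs from 51.0 − 49.5 = 1.5 to 51.0 − 45.4 = 5.6 points.

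**5. Mantel-Haenszel by severity.** RR = (0.588 + 1.449 + 3.304)/(5.353 + 14.410 + 15.848) = 5.342/35.611 = 0.150 (95% CI 0.090 to 0.251, contacts treated as independent). Risk difference = (35.611 − 5.342)/63.152 = 47.9 points. A logistic model with arm and severity gives an OR of 16.3 (8.2 to 32.2).

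**6. Check Table (4).** The univariate arm entry 12.533 is 188/15, the odds of protection within the ivermectin arm. Its printed interval, 7.408 to 21.205, is the interval for those odds. The crude OR is 17.6. The age entry, 205/65 = 3.154, is likewise odds within one level.

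In the multivariate column, age 60 or under has an OR for protection of 0.254 (0.101 to 0.639). Table (3) gives that age group more protection under ivermectin (93.8% v 84%) and nearly equal protection without it (41.3% v 44.4%). Rebuilt cells are 167/11 v 21/4 and 38/54 v 4/5, protected/ill. The Mantel-Haenszel OR stratified by arm = (167×4/203 + 38×5/101)/(11×21/203 + 54×4/101) = 5.172/3.277 = 1.58.

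**The case against.** **The documents already deal with severity.** Table (3) shows the arm effect in each severity level with p of 0.001 or less, and Table (4) adjusts for severity. An OR of 11.445 is more conservative than the 16.3 from adjusting for severity alone. This largely stands as a defence of the conclusion. It does not close the gap in reporting: Table (3) has no denominators and no pooled estimate, and Table (4) sets 12.533, which is not an odds ratio, beside 11.445. That pairing makes adjustment look almost without effect, when the like-for-like change is from 17.6 to 11.4.

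**The sentence under Table (1) is true.** It is, for the three variables it names. The criticism is of the omission, not of a false statement.

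**The shift is small.** The crude 95% CI for the RR, 0.076 to 0.211 with contacts treated as independent, contains 0.150. This stands, and it limits the weight of the point.

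**The imbalance may not be statistically secure.** With an assumed design effect of 4 its p-value is 0.089. This stands against any claim of significance. The bias in these data depends on the observed mix, not on that p-value.

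**The age odds ratio is a separate matter and may have an explanation.** The 1.58 is stratified by arm only. If every contact over 60 is assumed to have a comorbidity, a model with arm, age and comorbidity gives an age OR of about 0.62, so a value below 1 does not by itself contradict Table (3). That assumption does not reach 0.254, so the entry merits a check, but it does not prove the arm coefficient wrong.

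**Severity may not measure amount of exposure.** Illness is not graded by severity: contacts of mild cases fell ill more often than contacts of moderate cases in both arms. Contact time and isolation are not tabulated by arm, so a reader cannot infer that severity is the exposure factor tied most closely to illness.

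**Conclusion.** The point holds in a limited form. Index-case severity is unevenly distributed between the arms, Table (1) does not show it, and the lowest-risk stratum is over-represented under ivermectin. The crude 51.0-point difference is overstated by about 1.5 to 5.6 points, depending on the standard population.

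Two stronger readings should be resisted. A reader might infer that severity mix explains the result. It does not: protection is far higher under ivermectin in all three strata, and no direction or significance changes. A reader might also take 5.6 points as the size of the bias, but that is the top of the range and applies only to the ivermectin-arm mix.

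The conclusion rests on the rebuilt counts, which are unique and match every printed severity statistic, and on adjustment for severity alone. The point estimates do not depend on how contacts cluster. The interval 0.090 to 0.251 ignores clustering and is too narrow. This is a should-fix item.

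**What to change.** 1. Add index-case severity by arm to Table (1) (14/135/54 v 20/43/38, checked against the source data), and state that the arms were not balanced on it.
2. Report one internally consistent severity-adjusted contrast beside the crude one. Either standardise to all contacts (7.9% v 54.6%, difference 46.8 points, RR 0.144) or use Mantel-Haenszel (RR 0.150, difference 47.9 points). Do not mix estimators: 7.4% v 52.8% corresponds to an RR of 0.140, not 0.150.
3. Use standard errors that allow for clustering by index case.
4. Recheck and refit Table (4), replacing the within-level odds in the univariate column with odds ratios and verifying the age coefficient.
5. Tabulate contact time and place of isolation by arm. Using them as covariates is optional.

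The cost is one or two table rows and a re-analysis of data already held. The downside is a slightly less favourable headline and a wider interval.
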